2.2.2. Secondary Endpoints

- ACR20, ACR50 and ACR70 response rate at all time points.
- HAQ-DI score at all time points.
- Psoriatic Arthritis Response Criteria (PsARC) response at all time points.
- Physician's Global Assessment of Psoriasis (PGA-PsO) response at all time points.
- Psoriasis Area and Severity Index 75 (PASI75) response ie, the proportion of subjects achieving at least a 75% reduction in PASI relative to baseline (in this and/or prior study) and PASI/PASI component scores at all time points.
- Dactylitis severity score at all time points.
- Enthesitis score (using Spondyloarthritis Research Consortium of Canada (SPARCC) Enthesitis Index and Leeds Index) at all time points.
- Bath Ankylosing Spondylitis Disease Assessment Index (BASDAI) at all time points.
- Physical function/other patient reported outcomes to be assessed at Month 1, Month 6 (and every 6 months thereafter): Short-Form 36 (version 2, Acute); EQ5D; Functional Assessment of Chronic Illness Therapy-Fatigue (FACIT-F).

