2.2.3. Other Endpoints

- DAS28-3 C-reactive protein (CRP) at all time points.
- Psoriatic Arthritis Joint Activity Index (PsAJAI), Disease Activity Index for Reactive Arthritis/PsA (DAREA/DAPSA), Composite Psoriasis Disease Activity Index (CPDAI), Psoriatic Arthritis Disease Activity Score (PASDAS), Minimal Disease Activity (MDA) score and their components at all time points.
- Presence of dactylitis at all time points.
- Nail Psoriasis Severity Index (NAPSI) Score at Month 1, Month 6 (and every 6 months thereafter).
- Itch Severity Index (ISI) at Month 1, Month 6 (and every 6 months thereafter).
- Patient's Global Joint and Skin Assessment (PGJS-VAS) at all time points.
- Ankylosing Spondylitis Quality of Life questionnaire (ASQOL) at all time points.
- Physical function/other patient reported outcomes to be assessed at Month 1, Month 6 (and every 6 months thereafter): Dermatology Life Quality Index (DLQI); PsA Healthcare Resource Utilization Questionnaire (PsA HCRU); Work Limitations Questionnaire (WLQ).

- Incidence of investigator-reported clinically significant changes in physical examination from baseline (in this and/or prior study) during treatment.
- Incidence of electrocardiogram (ECG) abnormalities and change from baseline (in this and/or prior study) in ECG measurements during treatment.
- Incidence of vital sign (blood pressure and pulse rate) abnormalities and changes from baseline (in this and/or prior study) in vital sign measurements during treatment.

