6.2.2. Type B Visit: Months 3, 9, 15, 21, 27* and 33*

The window for the Month 3 visit is ± 7 days and ± 10 days for visits thereafter.

At the Month 3 visit only, subjects are required to fast for at least 9 hours prior to the visit. Blood collection may be taken up to 48 hours prior to or following this visit as necessary to ensure samples are collected in a fasted state.

All Patient Reported Outcomes should be completed prior to any other study procedures. These include the following:

- Patient's Assessment of Arthritis Pain (VAS).
- Patient's Global Assessment of Arthritis (VAS).
- BASDAI.
- ASQOL.
- Patient's Global Joint and Skin Assessment (PGJS-VAS).
- Health Assessment Questionnaire – Disability Index (HAQ-DI).

Procedures that will be performed include:

- Targeted physical examination (weight, examination of heart, lungs, abdomen, lower extremities, and lymph nodes).
- Vital signs: blood pressure, pulse rate and temperature (tympanic, oral or temporal preferred).

- Blood and urine specimen testing: Central laboratory tests including: Hematology, Chemistry Panel, Lymphocyte subset analysis (FACS), CRP, Urinalysis, Lipid panel (fasting) at Month 3 only.
- Urine Pregnancy Test (for women of women of childbearing potential only).
- Clinical Evaluation of Rheumatology Endpoints:
 - Tender/Painful Joint Counts (68);
 - Swollen Joint Count (66);
 - Physician's Global Assessment of Arthritis (VAS);
 - Assessment of presence and severity of dactylitis;
 - Assessment of enthesitis using the Spondyloarthritis Research Consortium of Canada [SPARCC] Enthesitis Index and Leeds Index.
- Clinical Evaluation of Dermatology Endpoints:
 - Physician's Global Assessment of Psoriasis (PGA-PsO);
 - Psoriasis Area and Severity Index (PASI);
 - Body Surface Area (BSA).
- Clinical Evaluation of Rheumatology and Dermatology Endpoint: Physician's Global Assessment of Psoriatic Arthritis (VAS).
- Monitoring of adverse events and concomitant treatments. Record any modifications, deletions or additions.
- Drug accountability.
- Drug dispensing.

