6.2.6. Early Termination Visit

Subjects are required to fast for at least 9 hours prior to the visit. Blood collection may be taken up to 48 hours prior to or following this visit as necessary to ensure samples are collected in a fasted state.

All Patient Reported Outcomes should be completed prior to any other study procedures. These include the following:

- Patient's Assessment of Arthritis Pain (VAS).
- Patient's Global Assessment of Arthritis (VAS).
- Health Assessment Questionnaire – Disability Index (HAQ-DI).
- Patient's Global Joint and Skin Assessment (PGJS-VAS).
- BASDAI.
- ASQOL.
- SF-36 Version 2 (Acute).
- DLQI.
- FACIT Fatigue Scale.
- EuroQol EQ-5D.

- ISI.
- WLQ.
- PsA-HCRU

Procedures that will be performed include:

- **Cardiovascular Risk Assessment:** smoking status, average weekly alcohol consumption and family history of premature coronary heart disease (see [Section 7.4](#)).
- **Complete Physical Examination:** weight, general appearance, skin (presence of rash), HEENT (head, eyes, ears, nose and throat), lungs (auscultation), heart (auscultation for presence of murmurs, gallops, rubs), extremity exam (presence of peripheral edema), abdomen (palpation and auscultation), neurologic (mental status, station, gait, reflexes, motor and sensory function, coordination) and lymph nodes.
- **Vital signs:** blood pressure, pulse rate and temperature (tympanic, oral or temporal preferred).
- **Blood and urine specimen testing:** Central laboratory tests including: Hematology, Chemistry Panel, Lymphocyte subset analysis (FACS), CRP, HbA1c, Lipid Profile (fasting), Urinalysis.
- Urine Pregnancy Test (for women of childbearing potential only).
- Waist and hips circumference.
- 12-lead electrocardiogram.
- Clinical Evaluation of Rheumatology Endpoints:
 - Tender/Painful Joint Counts (68);
 - Swollen Joint Count (66);
 - Physician's Global Assessment of Arthritis (VAS);
 - Assessment of presence and severity of dactylitis;
 - Assessment of enthesitis using the Spondyloarthritis Research Consortium of Canada [SPARCC] Enthesitis Index and Leeds Index.
- Clinical Evaluation of Dermatology Endpoints:
 - Physician's Global Assessment of Psoriasis (PGA-PsO);

- Psoriasis Area and Severity Index (PASI);
- Body Surface Area (BSA);
- Nail Psoriasis Severity Index (NAPSI).
- Clinical Evaluation of Rheumatology and Dermatology Endpoint: Physician's Global Assessment of Psoriatic Arthritis (VAS).

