10. APPENDICES

Appendix 1. Definition and Use of Visit Windows in Reporting

For reporting purposes, the following visit windows will be used for efficacy/PRO variables and for any safety displays that display by week/month. If two or more visits/observations fall into the same window, the visit/observation closest to the target day should be used in the analyses. If there is a tie, the later visit should be used. However, if two or more visits/observations fall in the same window, and the latest visit is the last visit of the study due to early termination, then this will be the visit used in the analysis for that visit window. Per the master visit schedule provided to the investigator sites, a month is defined as 4 weeks or 28 days.

Study day will be calculated as: date of assessment/collection – date of the first dose + 1.

Visit Label	Target Day	Definition [Day Window] - Lower	Definition [Day Window] - Upper
Screening		Prior to baseline visit	
Baseline		
The baseline values for the safety endpoints come from the baseline of the qualifying study for patients who enroll within 14 days of the last visit of the qualifying study. For the patients whose enrollment are out of 14-day window, their baseline values of the safety endpoints will be from the baseline visit of this study, A3921092.
 
The baseline values for all the efficacy or health-outcome endpoints come from the baseline of the qualifying study.
 
In addition, in the sensitivity analysis for the ACR response rates and ΔHAQ-DI, the baseline value will be the baseline visit for A3921092 for subjects whose enrollment is out of 14-day window.
 
Day 1 = date of first dose of study treatment taken of study A3921092.
	
Month 1	29	1*	57
Month 3	85	58	127
Month 6	169	128	211
Month 9	253	212	295
Month 12	337	296	379
Month 15	421	380	463
Month 18	505	464	547
Month 21	589	548	631
Month 24	673	632	715
Month 27	757	716	799
Month 30	841	800	883
Month 33	925	884	967
Month 36	1009	968	1051 (for safety) ≥969 (for efficacy and PRO)
Month 39**	1093	1052	1135
Month 42**	1177	1136	1219
Month 45**	1261	1220	1303
Month 48**	1345	≥1304	

*The lower limit of the Month 1 visit window will be Day 2 for safety analysis for subjects who enroll out of 14-day window of the last visit of the qualifying study.

**For safety endpoints summarized by visit such as laboratory value and vital signs data at a windowed visit only.

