Note some of the endpoints may not be measured at every visit. For example, SF-36v2, FACIT-F, EQ-5D-3L, PsA-HCRU, WLQ, DLQI, NAPSI and ISI will not be assessed at Months 3 per the study protocol and the visit window at Month 3 will be undefined. In the event that an observation falls into one of the undefined visit windows, that observation will not be used in analysis.

The following categories will be used in the treatment exposure and duration of treatment summaries. The duration will be calculated as: date of the last dose – date of the first dose +

1. Any missed doses/drug holidays will be ignored in the calculation.

Category (days)
1
2-14 (2 weeks)
15-28 (2 weeks-1 month)
29-84 (1-3 months)
85-168 (3-6 months)
169-252 (6-9 months)
253-336 (9-12 months)
337-504 (12-18 months)
505-672 (18-24 months)
673-840 (24-30 months)
841-1008 (30-36 months)
1009-1176 (36-42 months)
≥1177 (42-48 months)

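### For eight instruments collected six-monthly, the LTE window rule drops early-termination values that fall in windows with no scheduled assessment, about 47% of follow-up days

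*SAP*

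**What the plan says.** SAP Appendix 1 maps each LTE assessment to a month by study day. It then notes that certain instruments are skipped at some of the visits, as follows: "For example, SF-36v2, FACIT-F, EQ-5D-3L, PsA-HCRU, WLQ, DLQI, NAPSI and ISI will not be assessed at Months 3 per the study protocol". The Month 3 window is declared undefined for them, and the rule that follows is general: "In the event that an observation falls into one of the undefined visit windows, that observation will not be used in analysis".

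The protocol fixes the schedule. Protocol 2.2.2 has SF-36, EQ-5D and FACIT-F under "Physical function/other patient reported outcomes to be assessed at Month 1, Month 6 (and every 6 months thereafter", and Protocol 2.2.3 gives the same timing to DLQI, PsA-HCRU, WLQ, ISI and the nail score ("Nail Psoriasis Severity Index (NAPSI) Score at Month 1, Month 6 (and every 6 months thereafter"). The visits between are headed "6.2.2. Type B Visit: Months 3, 9, 15, 21, 27* and 33", and none of the eight instruments is on that visit's list. All eight are on the list in Protocol 6.2.6 (Early Termination Visit), with no condition on study day.

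Two other SAP rules bear on this:

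- **Precedence (Appendix 1).** If several observations share a window and the latest is the final visit because of early termination, that one is used, even if another lies closer to the target day.
- **Missing data (Section 7).** Missing endpoint values are not imputed in the descriptive summaries.

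**The concern.** The two protocol lists and the window rule do not fit together. The Early Termination visit is set up to capture these instruments when a subject leaves, but whether the value counts depends only on the calendar. A subject who leaves on Day 200 has a Month 6 value. One who leaves on Day 220 contributes nothing from that visit for these eight instruments. The precedence rule does not help, because it chooses among observations inside one window and cannot move a value out of an undefined one. It also points the other way in spirit, since it prefers the termination value wherever a window exists.

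The protocol withdraws subjects who need rescue for more than 10 consecutive days and recognises withdrawal for insufficient response. Some of the omitted values may therefore come from subjects doing poorly, and an observed-case table without them could look better than the cohort's experience.

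Two composites are also caught. PASDAS needs the SF-36 physical component and CPDAI needs the DLQI. Either score is missing if any component is missing, yet SAP 6.3 lists both for all time points. The SAP does not say what happens to them at a termination visit in an undefined window.

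**Working it through.** The plan states no percentage here, so there is no figure of its own to reproduce. The window table was checked first: target day = 28 × month + 1, and each boundary is the midpoint of adjacent targets. All 12 boundaries from Month 1 to Month 36 agree.

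**Undefined days** (length = upper − lower + 1, SAP Appendix 1):

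| Window | Days | Length |
|---|---|---|
| Month 3 | 58–127 | 70 |
| Month 9 | 212–295 | 84 |
| Month 15 | 380–463 | 84 |
| Month 21 | 548–631 | 84 |
| Month 27 | 716–799 | 84 |
| Month 33 | 884–967 | 84 |

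Total = 70 + 5 × 84 = 490 days.

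**Share of follow-up**

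- To Day 1051 (upper limit of Month 36 for safety; the efficacy window is open-ended): 490/1051 = 46.6%.
- To Day 1008 (36 × 28 days of treatment): 490/1008 = 48.6%.
- If only Month 3, the one window named, were undefined: 70/1051 = 6.7%.

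**From days to dropouts.** The documents give no LTE dropout rate or timing, so this step is an assumption. Take constant-hazard dropout with cumulative loss p by Day 1008, so that S(t) = exp(−ht) and h = −ln(1 − p)/1008. The share of dropouts leaving in an undefined window is Σ[S(lower − 1) − S(upper)] / [1 − S(1008)]. For p = 10% this is 48.5%; for p = 50% it is 48.1%.

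**Who is affected at one visit.** With even dropout, one 84-day window holds 84/1008 = 8.3% of dropouts. At p = 10% to 50% that is about 0.8% to 4.2% of enrolled subjects.

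**On-time visits are safe.** Month 1 within ±7 days, and Months 6, 12, 18, 24, 30 and 36 within ±10 days, all stay inside their own windows. The loss falls on early-termination and other off-schedule assessments.

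**The case against.** The strongest case for leaving the rule alone is that it is prespecified and has a purpose: it keeps off-schedule values from being labelled as a different month. It also avoids Month 27 or Month 33 rows made up of an unrepresentative few, since the sub-study baseline collects SF-36, FACIT-F and EQ-5D at those visits from sub-study entrants only. The LTE has no hypotheses, models or decision rules. Each dropout supplies one value to one visit and is absent afterwards, so later tables are shaped mainly by the lack of imputation, which no window rule changes. All of this stands. It limits the weight of the point but does not explain why a value the protocol sets out to collect should be unused.

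Several stronger readings are tempting, and the documents do not support them:

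- **That dropouts' last assessments are lost in general.** They are lost for eight instruments only. HAQ-DI, pain, patient global, BASDAI, ASQOL, PGJS-VAS, joint counts, PASI, BSA and PGA-PsO are collected at the in-between visits and keep their termination values. Among skin-related measures, only DLQI, ISI, NAPSI and possibly CPDAI are exposed.
- **That 47% of dropouts are affected.** The figure is a share of days.
- **That the SAP itself lists six undefined windows.** It names Month 3 as an example. Months 9 to 33 follow from that wording, the plural in the rule and the protocol schedule. This is the natural reading, but it is an inference.
- **That the results are biased favourably.** Direction is plausible; nothing in the documents establishes sign or size.

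A further fair objection concerns the obvious remedy, assignment to the nearest scheduled visit. In each undefined window the first 41 days would map back to the earlier visit (for example Days 212–252 to Month 6), which is 6 × 41 = 246 of the 490 days. The precedence rule would then let the termination value overwrite a valid on-schedule one. It would also split PASDAS and CPDAI components across months. That remedy should not be used.

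**Conclusion.** The point holds in limited form. For the eight listed instruments, termination values in the six undefined windows are collected and then left out of the LTE summaries. The windows cover 46.6% of days to Day 1051 (48.6% of 1008 treatment days), which means roughly half of terminations if timing is even. This rests on reading Months 9, 15, 21, 27 and 33 as undefined alongside Month 3; on the literal Month 3 reading the share is 6.7%, and the SAP then has no stated rule for the other five windows. Either way the text needs completing.

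The consequence is confined to descriptive secondary and other summaries, plus an unresolved status for PASDAS and CPDAI at termination. The primary safety endpoints are untouched. So is the sub-study, which has its own windows and collects SF-36, FACIT-F and EQ-5D at every scheduled post-baseline visit. The change is worth making before the final LTE analysis because it is cheap, but no main conclusion depends on it.

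**What to change.** In SAP Appendix 1, list the undefined windows for each instrument. Then add, as a sensitivity summary beside the planned table or as the main rule, text such as:

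> For SF-36v2, FACIT-F, EQ-5D-3L, PsA-HCRU, WLQ, DLQI, NAPSI and ISI, an early-termination observation in an undefined window is assigned to the next window at which the instrument is scheduled (Month 3 to 6, 9 to 12, 15 to 18, 21 to 24, 27 to 30, 33 to 36). It does not replace an on-schedule observation. PASDAS and CPDAI at early termination are derived from components collected at that same visit and assigned as a unit to the same window.

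Forward assignment avoids the overwriting problem, because a subject who has left will not normally have an on-schedule value in the next window.

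The cost is SAP text and programming; no new data are needed. The drawback is distance from the label day. A value on the first day of the Month 9 window is 337 − 212 = 125 days (about 18 weeks) before the Month 12 target, and the same gap applies to the later windows; for Month 3 it is 169 − 58 = 111 days. That is the reason to show it as a sensitivity table if the sponsor prefers to keep the planned summary as the main one.

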Appendix 2. Further Definition of Endpoints

Appendix 2.1. ACR Assessments

The American College of Rheumatology's definition for calculating improvement in RA (ACR20) is calculated as a $\geq 20\%$ improvement in tender and swollen joint counts and $\geq 20\%$ improvement in 3 of the 5 remaining ACR-core set measures: patient and physician global assessments, pain, disability, and an acute-phase reactant. Similarly, ACR50 and 70 are calculated with the respective percent improvement. This efficacy measurement will be made at every study visit. The specific components of the ACR Assessments that will be used in this study are:

Tender/Painful Joint count (68);

Swollen Joint Count (66);

Patient's Assessment of Arthritis Pain (VAS);

Patient's Global Assessment of Arthritis (VAS);

Physician's Global Assessment of Arthritis (VAS);

C-Reactive Protein (CRP in mg/L);

Health Assessment Questionnaire – Disability Index (HAQ-DI).

If the value in any of the components at a timepoint is missing, the component variables that are not missing will be used to determine the response status. As a general principle, if there are sufficient non-missing components to determine whether the ACR endpoint is a response or non-response, then ACR endpoint is not missing, else if the available non-missing components are not sufficient to determine the response status of ACR endpoint then it is considered missing.

In order to avoid numerical difficulty, if the baseline value of any component is equal to 0, the following algorithm will be used in evaluating the percent change from baseline:

1. If change from baseline is also equal to 0, then percent change from baseline is set to be 0%;
2. If change from baseline is > 0 , then percent change from baseline is set to be 999999%.

These percentages will be used to derive the ACR endpoints. Change from baseline cannot be < 0 since none of the components should have negative value.

Lower limit of quantification (LLOQ) for CRP is 0.020 mg/dL (or 0.200 mg/L). Any CRP value below the LLOQ will be reported as " <0.020 " in database and will be set to 0.019 mg/dL (0.190 mg/L) and used in analyses throughout. The unit for CRP will be mg/dL or mg/L depending on endpoint of interest. The upper limit of the normal range is 2.87 mg/L.

The VAS data will need to be rescaled prior to any calculation ([Section 6](#)).

Appendix 2.2. Health Assessment Questionnaire – Disability Index (HAQ-DI)

The HAQ-DI assesses the degree of difficulty a subject has experienced during the past week in 8 domains of daily living activities: dressing and grooming, arising, eating, walking, hygiene, reach, grip, and other activities. Each activity category or domain consists of 2-3 items. For each question in the questionnaire, the level of difficulty is scored from 0 to 3 with 0 representing “no difficulty,” 1 as “some difficulty,” 2 as “much difficulty,” and 3 as “unable to do”. The domain score for each domain is the maximum (ie, worst) of the scores from the items/questions within the domain. If this domain score is ≥ 2 , no further adjustment is needed. If it is < 2 (ie, 0 or 1) but no aids, devices or help from another person is indicated, then also no adjustment is needed. However, if it is < 2 and any aid, device or help from another person is indicated, then it is further adjusted upward to 2 as described below.

Any activity that requires assistance from another individual or requires the use of an aid or an assistive device adjusts to a minimum score of 2 to represent a more limited functional status.

Domain	If domain score is either 0 or 1, adjust to 2 when the following is satisfied.
Dressing and grooming	“Devices used for dressing (button hook, zipper pull, long-handled shoe horn, etc)” or help from others on “Dressing and Grooming” is checked
Arising	“Special or built up chair” or help from others on “Arising” is checked.
Eating	“Built up or special utensils” or help from others on “Eating” is checked.
Walking	“Cane”, “Walker”, “Crutches”, “Wheelchair”, or help form others on “Walking” is checked
Hygiene	“Raised toilet seat”, “Bathtub bar”, “Long-handled appliances in bathroom”, “Bathtub seat” or help from others on “Hygiene” is checked.
Reach	“Long-handled appliances for each” or help from others on “Reach” is checked
Grip	“Jar opener (for jars previously opened)” or help from others on “Gripping or opening things” is checked.
Activities	Help from others on “Errands and chores” is checked.
Note: For “Other, (specify)”, whether checked or unchecked or specifying the other “aids or devices” in this category, is not to be used in the adjustment of the domain score.	

For each domain, the domain score will be determined by non-missing scores from the questions. A domain score will only be missing if all scores within the domain are missing. The HAQ-DI score is the average of all the 8 domain scores. If > 2 domain scores are not complete or missing, HAQ-DI score is considered missing, else the HAQ-DI score is computed as the average of the non-missing domain scores (Bruce and Fries 2005).³

Change from baseline in HAQ-DI (Δ HAQ-DI) will be calculated.

HAQ-DI response will be defined as an improvement (ie, a decrease) from baseline of ≥ 0.30 and ≥ 0.35 (2 endpoints) in HAQ-DI scores.

